1 PROTOCOL SUMMARY

1.1 Synopsis

Short Title:

A clinical study to assess the local cutaneous and ocular tolerance of three developmental cosmetic facial skin care formulations.

Background and Rationale:

A cosmetic product that is freely available to the consumer must be safe when applied under normal or reasonably foreseeable conditions of use. Thus, as a general requirement, the safety of a developmental formulation should be confirmed before it is marketed.

Acceptability 'in-use' studies are useful clinical models which determine the irritation potential (local tolerance) of cosmetic formulations to provide confidence the finished products are suitable for general sale.

The objective of this clinical study is to determine the local cutaneous and ocular tolerance of three developmental cosmetic facial skin care products (a serum, a lotion and a cream) in healthy females with clinically assessed sensitive facial skin, under normal conditions of use.

Objectives and Endpoints:

Objective(s)	Endpoint(s)
Primary	
To evaluate the local cutaneous tolerance profile (dermatologist assessed) of the 3 investigational products in healthy females with sensitive facial skin under normal conditions of use after 21 days.	Proportion of subjects determined by a dermatologist to have a clinically relevant positive outcome for cutaneous irritation after 21 (+2) days of product use.
Secondary	
To evaluate the local ocular tolerance profile (ophthalmologist assessed) of the 3 investigational products in healthy females with sensitive facial skin under normal conditions of use after 21 days.	Proportion of subjects determined by an ophthalmologist to have a clinically relevant positive outcome for ocular irritation after 21 (+2) days of product use.
To evaluate the local cutaneous tolerance profile (subject assessed) of the 3 investigational products in healthy females with sensitive facial skin under normal conditions of use.	Change from baseline (prior to any product application) in subject self-assessment scores of signs and symptoms of cutaneous irritation 1-2 hours after first product application.
	Change from baseline (prior to any product application) in subject self-assessment scores of signs and symptoms of cutaneous irritation after 21 (+2) days of product use.
To evaluate the local ocular tolerance profile (subject assessed) of the 3 investigational products in healthy females with sensitive facial skin under normal conditions of use.	Change from baseline (prior to any product application) in subject self-assessment scores of signs and symptoms of ocular irritation 1-2 hours after first product application.

	Change from baseline (prior to any product application) in subject self-assessment scores of signs and symptoms of ocular irritation after 21 (+2) days of product use
Safety	
To evaluate the general safety of the 3 investigational products.	Frequency and severity of Adverse Events.

Study Design:

This is a randomized, evaluator-blind (dermatologist and ophthalmologist), 3-arm, parallel-group, single-center, clinical 'in-use' study to determine the local cutaneous and ocular tolerance of 3 developmental cosmetic facial skin care formulations (a serum, a lotion and a cream) in healthy female subjects aged 18 to 65 years (inclusive) with clinically evaluated sensitive facial skin, as determined by a positive response to a Lactic Acid Sting Test (LAST).

A sufficient number of subjects will be screened (approximately 350) to randomize approximately 150 subjects to ensure that at least 135 subjects (45 per arm) complete the study.

Subjects will be clinically assessed by a qualified dermatologist for a baseline clinical assessment of signs and symptoms of facial cutaneous irritation and by a qualified ophthalmologist for a baseline clinical assessment of the signs and symptoms of ocular irritation. Subjects will be asked to answer a series of self-assessment questions on the facial cutaneous and ocular signs and symptoms of tolerance prior to any product application.

Site personnel involved in any clinical assessments will not be involved in the dispensing of test products and will be blind to product allocation. All reasonable efforts will be made to ensure the same assessors evaluate the same subject. Subjects will be required not to divulge the identity of the test products they have been using to any assessor, unless required for adverse event reporting or other medical or safety reason.

For eligible subjects, the first application of their assigned product will be at the investigational site, under the supervision of a trained technician. Subjects will be asked to answer the same series of self-assessment questions again on the facial cutaneous and ocular signs and symptoms of tolerance 1-2 hours after first product application.

Subjects will then be instructed to apply their assigned product at home again the same evening and twice-daily for a total of 21 (+2) days, as part of their normal skin care routine. A paper diary will be provided to each subject to record the number of daily applications of product, from first application at the study site to final application at home. The final application of product will be at home on the morning of the final visit (Visit 3).

At the final visit (Visit 3), the dermatologist and ophthalmologist will conduct final clinical assessments of the signs and symptoms of cutaneous and ocular irritation, respectively. Subjects will also be asked to conduct final self-assessment of the signs and symptoms of facial cutaneous and ocular irritation. Subjects will return their completed diary and supplied product and will then be discharged from the study.

Study Products:

Subjects will be assigned to 1 of the 3 study products in accordance with the randomization schedule.

The investigational products are developmental formulations intended to be used as cosmetic facial skin care products (a serum, a lotion and a cream) by adult consumers with sensitive facial skin.

The instructions for use provided to subjects in this study are consistent with those intended to be communicated to consumers when the product is made freely available for purchase.

Type and Planned Number of Subjects:

Healthy female subjects aged 18 to 65 years (inclusive) with clinically evaluated sensitive facial skin, as determined by a positive response to a LAST, with signs or symptoms of facial cutaneous irritation and no clinical signs or symptoms of ocular irritation will be enrolled into this study. Female subjects with sensitive facial skin have been selected as they have a greater familiarization and habitual use of facial skin care products.

A sufficient number of subjects will be screened (approximately 350) to randomize approximately 150 subjects to ensure that at least 135 subjects (45 per arm) complete the study.

The sample size for this study has been selected based on clinical considerations and to ensure compliance with the Agência Nacional de Vigilância Sanitária (ANVISA) Guideline for the Safety Evaluation of Cosmetic Products (ANVISA, 2012) which mandates an investigational product be tested on at least 30 subjects.

Cosmetic manufacturers, even those with basic toxicologic testing and epidemiologic feedback on their products, are aware that 1-10% of all cosmetic users note and often complain of discomfort, primarily on the face (Maibach and Engasser, 1988). Therefore, if 10% or less of subjects in each treatment arm experience a significant increase in clinical signs of irritation as determined to be clinically relevant by a dermatologist, the product will be considered to have comparable tolerability to other commercially available cosmetic skin care products.

The focus of the statistical analysis will be the number of subjects determined by the dermatologist to have a clinically relevant positive outcome for cutaneous irritation, following 21 (+2) days of twice-daily product use. With 45 subjects completing each treatment arm and under an assumption of 4% incidence of clinically evaluated intolerance, each group has a 96.68% probability of observing less than 10% events in the study. All the groups are independent hence the probability that all three groups individually result in less than 10% events is 0.9668³, which equates to 0.9037, or a power of 90.4% that the study will result in all three groups having less than 10% of subjects with clinical intolerance.

1.2 Schedule of Activities

The schedule of activities table provides an overview of the subject visits and study procedures.

The investigator may schedule visits (unplanned visits) in addition to those listed on the schedule of activities, to conduct evaluations or assessments required to protect the well-being of the subject.

Table 1-1 Schedule of Activities

Procedure/Assessment	Screening	Randomization	Final Visit
	Visit 1 Day - 6 to 0	Visit 2 Baseline/Day 1 ^a	Visit 3 Day 21 (+ 2)
Informed Consent (date and time captured)	X		
Demographics	X		
Medical History	X		
Medications Review (current/concomitant)	X	X	X
Inclusion/Exclusion Criteria	X ^b	X ^c	
Lactic Acid Sting Test (LAST)	X		
Fitzpatrick Skin Type Assessment	X		
Subject Eligibility for Enrolment	X		
Clinical Assessment by Dermatologist		X	X
Clinical Assessment by Ophthalmologist		X	X
Subject Continued Eligibility		X	X
Subject Self-Assessment		X ^d	X
Randomization		X	
Product and Diary Dispensing		X	
Supervised Product Application		X ^e	
Adverse Events (AEs) Review^f	X	X	X
Product and Diary Return (Diary review)			X
Study Conclusion/Subject Exit from Study			X

Footnotes:

- a. Visit 1 and Visit 2 may be combined. If Visit 1 and Visit 2 are not combined, then Visit 2 must occur within 7 calendar days of Visit 1
- b. Inclusion criteria 1-5 and exclusion criteria 1-17 to be assessed at Visit 1
- c. Inclusion criteria 6-10 and exclusion criteria 18-23 to be assessed at Visit 2 (if visit 2 is not combined with visit 1)
- d. Subject self-assessment on Visit 2 will occur prior to randomization and product application (baseline) and 1-2 hours after first supervised product application
- e. If Visit 2 is combined with Visit 1, there should be a minimum of 30 minutes after the LAST has completed before the supervised product application.
- f. Adverse Events (AEs) and therefore all Serious Adverse Events (SAEs) will be collected immediately after a subject provides consent to participate in the study by completing the Informed Consent Form (ICF).

2 INTRODUCTION

2.1 Study Rationale

GSK CH has developed 3 new cosmetic skin care formulations (a serum, a lotion and a cream) intended to be suitable for use by adult consumers with sensitive facial skin. Clinical data are required to demonstrate that the developmental formulations have favorable local tolerance profiles in the target population under normal conditions of use, prior to commercialization.

Complete information for the developmental cosmetic facial serum, lotion and cream may be found in the single reference safety document (SRSD), which for this study is the Safety Statement.

2.2 Background

In recent years the cosmetic industry has grown considerably, along with its concern for developing safe and effective products. Heightened industry awareness, consumer and regulatory agency requirements have led cosmetic manufacturers to adopt procedures that provide a robust assessment of the risks and benefits of their products. This includes the conduct of clinical tests to assess safety and efficacy, which are often coordinated by dermatologists or other experts before marketing a new product. These procedures provide greater assurance of safety for cosmetic manufacturers, increasing their credibility and confidence among consumers.

A cosmetic product that is freely available to the consumer must be safe when applied under normal or reasonably foreseeable conditions of use. Thus, as a general requirement, the safety of a developmental formulation should be confirmed before it is marketed (Guideline for the Safety Evaluation of Cosmetic Products; Agência Nacional de Vigilância Sanitária (ANVISA), 2012; Cosmetics Europe, 2004).

Acceptability 'in-use' studies are useful clinical models to determine the irritation potential (local tolerance) of a cosmetic formulation to provide confidence an investigational product is suitable for general sale in the target population. Such studies aim to provide a clinical and subjective characterisation of the signs and symptoms of irritation following regular application of a topical product and often involve dermatologist and ophthalmologist oversight.

Sensitive skin may be characterized by sensations including stinging, burning and itching, often without any visible signs or symptoms. The absence of visible signs or symptoms of irritation presents a challenge in the diagnosis of sensitive skin. However, several substances are known to trigger an irritant response in people with sensitive skin, such as benzoic acid, cinnamic acid, non-ionic emulsifiers, sodium lauryl sulfate, lactic acid, propylene glycol, urea and sorbic acid (De Groot *et al*, 2010; Lundov *et al*, 2010). Therefore, a routine test to diagnose sensitive skin is a lactic acid sting test (LAST), whereby an aqueous solution of lactic acid is applied to the facial nasolabial fold to try and trigger a sensorial response, often alongside a placebo such as saline. The stinging sensation response to the irritant may be measured in a binary way (i.e. presence or absence) or with a magnitude scale (Farage *et al*, 2006). The LAST procedure allows for the characterization and enrollment of subjects with sensitive facial skin into clinical trials to enable the local tolerance of an investigational product to be investigated in this population.

2.3 Benefit/Risk Assessment

The 3 new cosmetic skin care formulations (a serum, a lotion and a cream) intended to be suitable for use by adult consumers with sensitive facial skin.

Complete information for these formulations may be found in the single reference safety document (SRSD), which for this study is the Safety Statement.

2.4 Mechanism of Action/Indication

Cosmetic products are preparations applied to the body, especially the face, intended to be applied for cleansing, beautifying, promoting attractiveness, or altering the appearance without affecting the body's structure or functions. The investigational products in this study are cosmetic facial skin care products (a serum, a lotion and a cream) that are intended to be applied topically to the face by healthy female subjects with sensitive facial skin, immediately after cleansing, with the intent of delivering ingredients directly onto the skin.

The European Union Cosmetics Directive defines a cosmetic as any substance or preparation intended to be placed in contact with the external parts of the human body with a view exclusively or mainly to cleaning, perfuming, changing appearance and/or correcting body odours and/or protecting or keeping in good condition (European Commission (EC), 2009). This is a consistent definition of cosmetic products per ANVISA (ANVISA, 2012)

3 STUDY OBJECTIVES AND ENDPOINTS

Table 3-1 Study Objectives and Endpoints

Objective(s)	Endpoint(s)
Primary	
To evaluate the local cutaneous tolerance profile (dermatologist assessed) of the 3 investigational products in healthy females with sensitive facial skin under normal conditions of use after 21 days.	Proportion of subjects determined by a dermatologist to have a clinically relevant positive outcome for cutaneous irritation after 21 (+2) days of product use.
Secondary	
To evaluate the local ocular tolerance profile (ophthalmologist assessed) of the 3 investigational products in healthy females with sensitive facial skin under normal conditions of use after 21 days.	Proportion of subjects determined by an ophthalmologist to have a clinically relevant positive outcome for ocular irritation after 21 (+2) days of product use.
To evaluate the local cutaneous tolerance profile (subject assessed) of the 3 investigational products in healthy females with sensitive facial skin under normal conditions of use.	Change from baseline (prior to any product application) in subject self-assessment scores of signs and symptoms of cutaneous irritation 1-2 hours after first product application.
	Change from baseline (prior to any product application) in subject self-assessment scores of signs and symptoms of cutaneous irritation after 21 (+2) days of product use.
To evaluate the local ocular tolerance profile (subject assessed) of the 3 investigational products in healthy females with sensitive facial skin under normal conditions of use.	Change from baseline (prior to any product application) in subject self-assessment scores of signs and symptoms of ocular irritation 1-2 hours after first product

	application. Change from baseline (prior to any product application) in subject self-assessment scores of signs and symptoms of ocular irritation after 21 (+2) days of product use
Safety	
To evaluate the general safety of the 3 investigational products.	Frequency and severity of Adverse Events.

The objective of this clinical study is to evaluate the local tolerance profile of 3 developmental skin care products; a serum, a lotion and a cream, in healthy females with clinically assessed sensitive facial skin under normal conditions of use.

Cosmetic manufacturers, even those with basic toxicologic testing and epidemiologic feedback on their products, are aware that 1-10% of all cosmetic users note and often complain of discomfort, primarily on the face (Maibach and Engasser, 1988). Therefore, if 10% or less of subjects in each treatment arm experience a significant increase in clinical signs of irritation as determined by a dermatologist, the product will be considered to have comparable tolerability to other commercially available cosmetic skin care products.

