12.3.1 Primary Analysis(es)

The primary endpoint within each group will be the proportion (number and percentage) of subjects determined by a dermatologist to have a clinically relevant positive outcome for cutaneous irritation after 21 (+2) days of product use, which is defined as an increase in total cutaneous irritation score versus baseline and dermatologist characterization as a clinically-relevant positive outcome at Visit 3 (Final Visit).

This is a non-comparative study and the three, separate, within group assessments will form the primary analysis. No comparison between groups will be made. No formal statistical inference will be performed.

The primary analysis will be performed using the Safety population.

In addition, the individual attribute responses and the total score will be listed for each subject by visit and by treatment group.

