Cosmetic manufacturers, even those with basic toxicologic testing and epidemiologic feedback on their products, are aware that 1 to 10% of all cosmetic users note and often complain of discomfort, primarily on the face. Therefore, if 10% or less of subjects in each treatment arm experience a significant increase in clinical signs of irritation as determined by a dermatologist, the product will be considered to have comparable tolerability to other commercially available cosmetic skin care products.

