In addition, the individual attribute responses, total score, change from baseline, clinical relevance and narratives will be listed (PPD) for each subject by visit and by study product.

4.5.1.2 Secondary Endpoint Variable 2

The other secondary endpoints will be change from baseline (prior to any product application) in the total subject self-assessment scores for signs and symptoms of cutaneous irritation at 1 to 2 hours after first product application and 21 (+2) days of twice daily product use. It will be summarized by number and percentage of subjects by visit for each study product and overall in PPD.

Calculations of subject self-assessment of sign and symptoms of cutaneous irritation total score and changes from baseline in total score:

Subject self-assessment of sign and symptoms of cutaneous irritation total score = cutaneous response score of redness + cutaneous response score of dryness + cutaneous response score of itching + cutaneous response score of stinging/burning + cutaneous response score of tightness

Change from baseline in subject self-assessment of sign and symptoms of cutaneous irritation total score at 1 to 2 hours = total cutaneous score at 1 to 2 hours – total cutaneous score at baseline

Change from baseline in subject self-assessment of sign and symptoms of cutaneous irritation total score at Day 21(+2) = total cutaneous score at day 21 (+2) – total cutaneous score at baseline

Where, the subject self-assessment of cutaneous response score is described in the Table 4-4

Table 4-4 Subject Self-Assessment Scale for Signs and Symptoms of Cutaneous Irritation

Attribute	Description (Score)				
Redness	None (0)	Very Slight (0.5)	Slight (1)	Moderate (2)	Severe (3)
Dryness	None (0)	Very Slight (0.5)	Slight (1)	Moderate (2)	Severe (3)
Stinging/Burning	None (0)	Very Slight (0.5)	Slight (1)	Moderate (2)	Severe (3)
Itching	None (0)	Very Slight (0.5)	Slight (1)	Moderate (2)	Severe (3)
Tightness	None (0)	Very Slight (0.5)	Slight (1)	Moderate (2)	Severe (3)

The individual cutaneous attribute responses, total score and change from baseline in total score will be listed for each subject by visit and by study product (PPD).

4.5.1.3 Secondary Endpoint Variable 3

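### The 10% limit comes from user-noted discomfort but is applied to a different outcome in a different population, so meeting it does not show comparability with marketed products

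*Protocol*

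**What the plan says.** Protocol 3 gives the basis for the limit: "1-10% of all cosmetic users note and often complain of discomfort, primarily on the face". SAP 1.2 repeats it ("1 to 10% of all cosmetic users note and often complain of discomfort"). The next sentence turns the range into a rule: "if 10% or less of subjects in each treatment arm experience a significant increase in clinical signs of irritation as determined by a dermatologist", then "the product will be considered to have comparable tolerability to other commercially available cosmetic skin care products". Protocol 1.1 carries the same reasoning and adds that the increase must be judged clinically relevant.

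The event being counted is set out in Protocol 12.3.1: "which is defined as an increase in total cutaneous irritation score versus baseline and dermatologist characterization as a clinically-relevant positive outcome at Visit 3". SAP 4.4.1.1 agrees and records the judgement as Yes/No. The total is the sum of four attributes graded by eye: erythema, dryness, scaling and edema (Protocol 4.1 and 9.2.1). Protocol 12.3.1 also calls the study non-comparative and plans no formal inference.

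Protocol 2.2 describes sensitive skin in terms of "sensations including stinging, burning and itching, often without any visible signs or symptoms". What subjects feel is collected separately, as a secondary endpoint with five cutaneous items (Protocol 9.2.3). SAP 4.5.1.2 has the change in that total "summarized by number and percentage of subjects by visit for each study product and overall". Neither document sets a limit for it.

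**The concern.** The 10% figure describes one quantity and is used to judge another. The documents do not link the two: they give no rate of dermatologist-judged reactions for marketed products, no conversion from discomfort to visible reaction, and no marketed-product arm. The comparability conclusion rests wholly on the borrowed figure.

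What is at stake is the statement made about each product, not the estimate. The observed proportion of adjudicated reactions is a valid description of visible tolerance. A reader told that a product is comparable to marketed products will take that to cover how it feels on sensitive skin as well, and the criterion does not measure that.

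**Working it through.** **1. The plan's own figure.** Inputs from Protocol 12.1: 45 completers per arm and a 4% true event rate. Since 10% of 45 is 4.5, passing means at most 4 events. The exact binomial gives P(X ≤ 4 | n = 45, p = 0.04) = 0.9668, and 0.9668³ = 0.9037. Both match the stated 96.68% and 90.4%. The arithmetic is right; the question is what the limit is compared with.

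**2. Benchmark and criterion side by side.**

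| | Benchmark (Protocol 3) | Criterion (Protocol 12.3.1, 9.2.1) |
|---|---|---|
| Who reports | The user | A dermatologist |
| What counts | Discomfort noted, often complained of | Rise in a visual four-item total, judged clinically relevant |
| When | Not stated | Visit 3 only |
| Population | All cosmetic users | LAST-positive women with erythema and dryness of at least 0.5 (Protocol 5.2) |

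**3. What cannot count as an event.**
- Stinging/burning, itching and tightness are not in the dermatologist's total. Alone they cannot trigger an event, and Protocol 2.2 says such sensations often lack visible signs.
- Discomfort at 1-2 hours that has gone by Visit 3 is not counted.
- The total is a net score. Dryness falling from 0.5 to 0 with erythema rising from 0.5 to 1 gives a change of −0.5 + 0.5 = 0, so no judgement is called for.

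**4. What works the other way.** A visible reaction can be scored without the subject noticing discomfort. The enrolled women were selected for sensitive skin and may react more often than cosmetic users in general.

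**5. Consequence for the pass probability.** Let D be the product's discomfort rate among all users, r the ratio of the discomfort rate in the trial population to D, and f the ratio of adjudicated events to discomfort in the trial. The adjudicated rate is a = D × r × f. The documents give neither r nor f. Because unnoticed visible reactions add to the numerator, f is not strictly capped at 1. The probability that one arm passes is P(X ≤ 4 | 45, a):

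| a | 2% | 4% | 5% | 6% | 8% | 10% | 15% | 20% |
|---|---|---|---|---|---|---|---|---|
| P(pass) | 99.8% | 96.7% | 92.7% | 86.9% | 71.0% | 52.7% | 17.5% | 3.8% |

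Take D = 10%, the top of the benchmark range, and assume f = 0.5:
- r = 1: a = 0.10 × 1 × 0.5 = 5%, pass 92.7%
- r = 2: a = 10%, pass 52.7%, the same as if the limit were applied to discomfort itself at 10%
- r = 3: a = 15%, pass 17.5%

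The rule is more lenient than a matched one when r × f is below 1 and stricter when it is above 1.

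**The case against.** A reader might infer that the primary event is a subset of noticed discomfort, so that the rule is lenient by construction and lets through products that irritate well over 10% of users. Figures can be produced for this. With an assumed 15% discomfort in the trial and f = 0.3, 0.5 or 0.6, the pass probability is 95%, 75% or 62%, against 17% for a limit on discomfort itself. With 20% it is 87%, 53% or 36%, against 4%. The binomial values are correct, but both inputs are assumed. The documents do not make the two outcomes nested, and choosing a sensitive, already symptomatic population may push event rates upward. This objection stands: leniency is possible but not shown.

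A second objection is that subject-assessed tolerance is already reported at both time points under SAP 4.5.1.2, so frequent discomfort would not be hidden. That is largely right, although the display layouts are redacted and the documents state no responder definition. It does not repair the conclusion, because the comparability rule makes no use of that endpoint.

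Third, the 10% statement is a yardstick in the objectives, and the analysis sections contain no pass/fail test. That limits the seriousness. It does not make the inference valid, since the documents say what will be concluded when the yardstick is met.

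Finally, the source of the range is seen only as a one-line paraphrase. If its notion of discomfort included visible irritation, the outcomes would be closer. The population difference and the lack of a marketed-product rate on the adjudicated endpoint would remain.

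**Conclusion.** The concern holds as a mismatch of outcome and population that leaves the comparability conclusion unsupported. This follows from the documents' wording alone and needs no assumption about rates. Its net direction and size cannot be determined: at 10% discomfort among all users, the pass probability per arm runs from 92.7% to 17.5% over the assumed values of r × f from 0.5 to 1.5. What can be said with certainty is that sensations without visible signs, which the protocol describes as common in sensitive skin, cannot count towards the limit.

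The primary estimate, the sample-size figure and the use of 10% as a sponsor criterion are unaffected.

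**What to change.** In Protocol 1.1 and 3 and in SAP 1.2, replace the comparability conclusion with: *10% or less of subjects had a dermatologist-judged clinically relevant cutaneous reaction at Day 21 (+2)*. Keep 10% as a sponsor criterion. The comparability wording could stay only if the limit is justified with marketed-product data on the same adjudicated endpoint.

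Optionally, in SAP 4.5.1.2, report per product the number and percentage of subjects with an increase in self-assessed cutaneous symptoms at 1-2 hours and at Day 21 (+2), beside the primary result. This should be descriptive context only, with no pass limit.

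The comparability claim should not be moved to that proportion. It may look like the matching measure, but a rise on any of five prompted items in a sensitive-skin sample is not what the benchmark describes either. Assuming independent items, a chance rise of 2% per item gives 1 − 0.98⁵ = 9.6% of subjects with a rise at one time point, and 5% per item gives 1 − 0.95⁵ = 22.6%, with no product effect at all.

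The cost is a wording change and, if wanted, one table from data already collected. The downside for the sponsor is a narrower claim.
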